5. Added PROMIS Psychosocial Illness Impact Positive measure as part of main phase measures.
6. Updated Blinded/Unblinded Research Staff list to reflect current group leaders.

Version Number: 12

Version Date: 03-12-17

Summary of Revisions Made:

1. Clarified language pertaining to the timing of the formal screening process.
2. Revised our procedures regarding the timing of the initial telephone call following the mailing of the approach letter to prospective subjects.
3. Clarified language pertaining to the credentialed providers who would be leading the groups. There are providers from a variety of disciplines who may lead groups.
4. Added the option of sending text reminders for participants who request this type of communication rather than a telephone call.
5. Added a reminder letter that would be mailed prior to follow-up assessments.

Version Number: 13

Version Date: 06-21-17

Summary of Revisions Made:

1. Revised wording of sex/gender as a demographic variable collected/ used for stratification in randomization from "sex" to "sex/gender" to be more accurate of data collected/used.
2. Revised wording to reflect actual intention of collecting sleep baseline data before treatment starts rather than prior to randomization.
3. Revised wording to reflect actual intention of administering the Modified Stanford Hypnotic Clinical Scale (SHCS) before treatment starts rather than prior to randomization.
4. Updated language to reflect that data collected as part of the sleep sub-study will be collected up to 7 days during each assessment period.
5. Update language to indicate clinicians will not have access to the crosswalk between study data and participants' identities.
6. Deleted incorrect language making reference to the transcription of treatment data on to a new CRF with SUBID only; study sponsor gave study researchers permission not to transcribe data but rather have only electronic copies of the original forms saved on a secure clinical drive.
7. Add [name] to the list of study staff members.
8. Remove [name], [name], [name] and [name] from study staff members.
9. Eliminated incorrect reference to staff not reviewing treatment data of non-research participants; staff may review the form to ensure no adverse events take place that would require clinical intervention.
10. Corrected language in Table 3 regarding timing of pre-treatment brain activity assessment.

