Participants will be randomly assigned to 8 group sessions of (1) self-hypnosis (HYP), (2) mindfulness meditation (MM), or (3) an education control condition (ED). Treatment groups will meet once per week over an 8 week period. Each session will last for duration of about 90 minutes. Primary (characteristic pain intensity) and secondary outcomes will be assessed at pre-treatment, three times during treatment, post-treatment, and at 3- and 6-month follow-up. The total time involved in the study is approximately 20-23 hours over a 9-month period.

Once participants complete their involvement in the primary study (i.e., after they have received one of the treatments and completed their last follow-up assessment), they may be invited to attend either (or ultimately both, if they wish) of the other two group treatments. This is called the “open label” phase of the study.

Participants who attend treatment for the first time in cohort 10 and all subsequent cohorts will not be offered the open label phase given study researchers intend to stop running treatment groups by the time these participants will complete the main phase of the study. Instead, these participants will be offered the treatment materials for the treatment of their choice. The treatment materials (workbook and audio recordings) will be mailed via USPS.

Participants who were randomized in cohorts 1-9 and are eligible to participate in the open label phase for cohorts 11 or 12 will be offered the option of either receiving treatment materials in the mail for the treatment of their choice or enrolling in the open label phase depending on space availability.

Sub-Study:

All participants enrolled in the sleep sub-study will be asked to wear a wrist actigraph (Actiwatch 2, Philips Respironics, Bend, OR) for up to 7 consecutive days, up to 24 hours/day to collect objective sleep data at 3 time points: before treatment begins, immediately following the end of treatment, and 3 months following the end of treatment. During each one-week assessment period they will also be asked to complete a brief questionnaire each morning and evening, and fill out a sleep log that includes estimates of time to bed, time to sleep, time awake and out of bed, sleep quality, and daytime napping.

Sample Size and Population

Main Study:

We plan to enroll up to ~~343~~ 355** Veterans with moderate to severe chronic pain to achieve a sample size of 240 completers, with 80 completers in each of the treatment groups.

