Enrolled participants who complete the required baseline components (cognitive assessment, hypnotic and relaxation exercise, baseline data and demographic form, and pre-treatment assessment period) will be randomized in stratified blocks to ensure that participants with each sex/gender and pain type (neuropathic, non-neuropathic, mixed or undetermined) have an equal chance of being randomized to one of the 3 conditions. Stratifying in this manner will ensure the groups are balanced to reduce variation in outcome that is associated with each stratification variable.

Sub-Study:

Recruitment will follow the protocol of the main study. We propose to recruit up to ~~135~~ 180* 195** of the ~~343~~ 355** parent grant participants in order to ensure complete data from 117 participants, assuming a 15% drop-out rate. Based on our experience, we anticipate that at least 75% of the parent sample will elect to join the sleep study.

*Due to a higher attrition rate than anticipated, we have increased the enrollment number from 135 to 180 to ensure the 117 completers needed. A 13% attrition rate was determined based on the main study. The actual attrition rate for the sleep study is 27%.

** Enrollment number increased to allow for the recruitment of a full cohort in the final cohort of the study.

A. SPECIFIC AIMS

A1. Problem Statement

Main Study:

As many as 50% of male and 75% of female Veterans presenting to Primary Care report chronic pain¹⁻⁴, and reporting rates are even higher in specialty clinics.⁵⁻⁷ Among Veterans returning from Iraq and Afghanistan, 82% report chronic pain,⁸ and the prevalence of painful musculoskeletal, joint, and back problems tends to increase in the years following deployment.⁹ Prevalent co-morbidities among Veterans, such as substance use disorders, sleep dysregulation, mood disorders, and Post Traumatic Stress Disorder (PTSD) can amplify the experience of pain and complicate treatment.¹⁰⁻¹² In Veterans, the presence of co-morbid pain and anxiety is associated with increased service utilization,¹³ while co-morbid pain and substance use increases the risk of medication misuse.¹⁴ Pain is also associated with greater depression and anxiety,¹⁵ sleep dysregulation^{12, 16}, decreased quality of life,¹⁷ and lower self-reported health.¹⁸

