The sample for the sub-study will include up to ~~135~~ ~~180~~ 195 Veterans with chronic pain who are enrolled in an existing 3-arm RCT examining the efficacy and mechanisms of two active treatments (mindfulness meditation and self-hypnosis training), relative to a pain education control condition. At the time of recruitment into the parent study, all participants will receive information on the supplemental sleep study and be invited to join. If they agree, after consenting to the parent study, a research staff member (trained by [name], the lead on the supplemental study) will explain the sleep study and review the eligibility criteria and consent form specific to this study. Use of wrist actigraphy will be demonstrated and the additional sleep data collection will be explained. Once consented, participants who have agreed to participate will have additional self-reported sleep data collected along with the original RCT's planned pre-treatment assessments. As a condition of the parent grant, study participants will then be randomly assigned to eight group sessions of one of three standardized treatment conditions.

All participants enrolled in the sleep study will be asked to wear a wrist actigraph (Actiwatch 2, Philips Respironics, Bend, OR) for up to 7 consecutive days, up to 24 hours/day to collect objective sleep data at 3 time points, following study enrollment. During that one-week period they will also be asked to complete a brief questionnaire each morning and evening, and fill out a sleep log that includes estimates of time to bed, time to sleep, time awake and out of bed, sleep quality, and daytime napping. Participants will also call in to a voice mail system daily for up to 7 days to report their sleep and wake times.

These data (sleep/wake diary, sleep calls) will help validate the actigraph objective sleep data, assure participant engagement with sleep data collection, and serve as additional covariate and mechanism variables to explain sleep findings more completely.

These additional sleep data (self-reported sleep data via telephone, objective actigraph data, sleep/wake diary, sleep calls) will be collected at time points that align with significant data collection time points from the parent grant: immediately pre-treatment, treatment mid-point at week 4 (self-report data via telephone only), post-treatment at week 8 for assessment of post-treatment effect, and again at month 3 for a long-term measurement.

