Table 2. Study Design: Open Label Phase (for participants enrolled in cohorts 1-9)

Step	Data Collected	How Often/When
Pre-Treatment Telephone Assessments	Average pain intensity (primary outcome), depression, anxiety, sleep disturbance, pain interference, global health, post-traumatic stress, and medication use, cognition	After completion of 6 month assessment of main phase, before treatment begins
Treatment Intervention Selection	No data collected	Once following completion of pre-treatment assessments
Treatment	Homework completed between sessions, pain and comfort levels pre- and post-session, participant engagement as per clinician	Eight sessions avg. once per week

Post-Treatment Telephone Assessment	Average pain intensity (primary outcome), depression, anxiety, sleep disturbance, global health, pain interference, post-traumatic stress, medication use, global satisfaction, and treatment satisfaction, cognition	Once following end of treatment
--	---	---------------------------------

Table 3. Study Design: Sleep Sub-Study

Step	Data Collected	How Often/When
Pre-Treatment Telephone Assessments	Two questions about how much the subject agrees with certain statements about his/her sleep, as well as two questions about how confident the subject is about carrying our certain sleep behaviors	Once following consent, before treatment begins
Pre-Treatment Actigraph Device and Sleep/Wake Diary	Sleep duration and quality (objective and self-report), wake/ sleep times (self-report), how the subject felt that day, any problems s/he experienced such as illness or discomfort, and basic activities s/he participated in like going to work, napping, drinking caffeinated beverages, etc. (self-report)	One-week period following consent, before treatment begins
4 Week Telephone Assessments	Two questions about how much the subject agrees with certain statements about his/her sleep, as well as two questions about how confident the subject is about carrying our certain sleep behaviors	One-week period following treatment session #4
Post-Treatment Telephone Assessment	Two questions about how much the subject agrees with certain statements about his/her sleep, as well as two questions about how confident the subject is about carrying our certain sleep behaviors	Once after the end of treatment

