Assignment to one of the 3 groups will be accomplished with a Microsoft Excel spreadsheet with random numbers created by the research manager with the guidance of the biostatistician. Only a research staff member who does not have access to study data during subject enrollment will conduct the randomization procedures. This randomization assignment will be entered into a password-protected database located on a VA secure drive. Research staff will complete a randomization case report form for each randomized subject that will be filed with study data.

The staff randomizing subjects will convey assignment to [name] via email with only a code number used i.e. no identifying information to identify the participant. [name] will then update the master list of participants, both research and non-research, of the clinic portion of the program.

Subjects will be sent a letter that outlines the schedule of treatment sessions they will attend.

Research staff will re-screen participants on approved mutable eligibility criteria (e.g. pain intensity, frequency, etc.) if 6 months or more has elapsed between the consent process and randomization.

Randomization may take place up to four weeks prior to the start of the treatment groups for that particular cohort.

D6m. Treatment Scheduling: Research and Non-Research Participants

Cohorts of study treatment groups will be offered beginning every four months. In each 4-month period, there will be two class options for each condition, one based in Seattle and one at American Lake. Thus, there will be six classes offered per four month period, or a total of 18 classes per year.

Trained instructors will commit to offering three groups per year: one of each treatment type. This will reduce the potential for therapist bias in on the outcomes. Up to 15 participants can be enrolled in each group treatment class.

[name] will maintain lists of group assignments (for both research and non-research participants) and coordinate the scheduling of group class appointments. Both [name] and the unblinded research staff member responsible for randomization will have access to this information and be available to provide back-up if [name] is absent or preoccupied.

As aforementioned, the research staff conducting randomization procedures will alert [name] that a research participant has been randomized.

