We base our power calculation on a previous study that is informative of the statistical power found in sleep duration data from wrist actigraphy as collected in naturalistic repeated-measures settings. In this previous study, 24 regional airline pilots participated in a two-day flight simulator study.¹⁰⁷ In the day before the study, they flew into the airport where the flight simulator center was located, and that night they planned their sleep naturalistically. As the pilots discovered that the workload during the study was high, they extended their sleep in the night between the two study days in order to recuperate. As measured by wrist actigraphy (same type as will be used in the supplement), the sleep duration in the night prior to the second study day was significantly greater than the sleep duration in the night prior to the first study day, by a difference of 1.35 hours ($t_{23}=3.97$, $P<0.001$). The correlation of sleep duration between nights was $\rho=0.122$. Relevant for our power calculation is also the systematic between-subjects standard deviation, which was $SD=26.3$ minutes.

In aim 1 of the supplemental study, we will use wrist actigraphy to compare sleep pre-treatment to immediately post-treatment (8 weeks) and to 3-month follow-up, relative to sleep at the same time points in the control group. Thus, we will make two repeated-measures comparisons: pre-treatment to post-treatment in the intervention group relative to the control group, and pre-treatment to 3-month follow-up in the intervention group relative to the control group. Because each of these two comparisons defines an interaction effect, which is inherently low on statistical power, we set the a-priori type I error threshold to $\alpha=0.1$.¹⁰⁸ However, because we will do two comparisons using the same pre-treatment data, we must also control for multiple comparisons. Therefore, after applying Bonferroni correction, we end up with a type I error threshold of $\alpha=0.05$.

To make use of the statistical power conferred by systematic between-subjects variability,¹⁰² we will employ mixed-effects ANOVA to implement the test (which then again takes the form of an interaction effect).

For power calculation purposes this is relevant in that the standard deviation of interest is therefore the systematic between-subjects standard deviation provided above (which, in a comparison between independent samples, serves as the estimated pooled standard deviation).

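### The sub-study's pre-treatment sleep week may follow randomisation, when participants probably know their arm, so the baseline for its change contrasts can be biased

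*Combined protocol and SAP*

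**What the plan says.** **Timing of the sleep week.** The Précis (Interventions and Duration, Sub-Study) has the actigraph worn to obtain "objective sleep data at 3 time points: before treatment begins, immediately following the end of treatment, and 3 months following the end of treatment". The sleep sub-study design table in section D1 places the first actigraph and diary week in a "One-week period following consent, before treatment begins". Section D6s, under both the diary and the actigraph headings, says after enrolment and before treatment starts. The Version 13 entry in the revision history gives the intention as "collecting sleep baseline data before treatment starts rather than prior to randomization". The current wording carries that change.

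**What must precede randomisation.** In the Précis (Sample Size and Population), those who "complete the required baseline components (cognitive assessment, hypnotic and relaxation exercise, baseline data and demographic form, and pre-treatment assessment period) will be randomized". Section D6l repeats the list. Neither place names actigraphy or the sleep diary.

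**What follows randomisation.** Section D6l allows randomisation up to four weeks before the cohort's groups begin, and adds: "Subjects will be sent a letter that outlines the schedule of treatment sessions they will attend".

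**Text that implies the opposite order.** In section D1, the main-study synopsis randomises participants once all baseline assessments are done, and Table 1 places randomisation after all baseline procedures. The sub-study synopsis collects self-reported sleep data with the pre-treatment assessments and says "study participants will then be randomly assigned to eight group sessions of one of three standardized treatment conditions".

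**Use of the baseline.** The sub-study part of Statistical Analyses names self-reported sleep quality and actigraphic sleep duration as primary outcomes for Aim 1. The sub-study power section describes the first comparison as "pre-treatment to post-treatment in the intervention group relative to the control group", and the second in the same way at 3 months.

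**The concern.** A baseline taken before allocation cannot be influenced by the arm. A baseline taken after the participant knows the arm can be: sleep ratings, and to a lesser degree sleep behaviour, may respond to hope or disappointment about the class assigned. In a contrast of change between arms, a difference created at baseline carries into the result with the opposite sign, to the extent that it has gone by the later measurement. It could produce an apparent sleep benefit for self-hypnosis or mindfulness, or hide a real one. The repeat rule in section D6s adds to the opportunity. The sleep week may be redone when treatment has not started within four weeks, with no link to randomisation and no rule on which week then serves as baseline.

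**Working it through.** **1. Can the week fall after notice?** The sleep week lasts up to 7 days. The gap between randomisation and the first class may be up to four weeks (28 days). The week therefore fits inside the gap, and no rule excludes that.

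**2. Does the participant know the arm by then?** The documents do not say that the letter names the arm. It gives the schedule of the assigned sessions. Section D6m runs separate classes for each condition at each site, section D6n puts the sessions on the Veteran's regular appointment list, and no text provides for withholding the assignment. Knowledge of the arm is a probable inference.

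**3. The plan's own sample size.** Inputs from the sub-study power section: effect 15 min, SD 26.3 min, one-sided alpha 0.05, power 80%.

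- n per arm = 2 × [26.3 × (1.645 + 0.842) / 15]² = 38.01, rounded up to 39. This reproduces the stated 39 per group and 117 in total.
- Power at 39 per arm is 0.809 by the normal approximation and 0.803 by the noncentral t.

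**4. Standard error on the same basis.** SE = 26.3 × √(2/39) = 5.96 min.

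**5. Illustration.** Let b be the average difference between an active arm and control at baseline that arises only because the arm is known. The documents give no value, so b is an assumption. It is also assumed that none of the shift remains at the later time point.

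- If the active arm's baseline is lower by b, type I error = 1 − Φ(1.645 − b/5.96). This gives 7.0% for b = 1 min, 9.5% for 2 min, 12.7% for 3 min and 21.0% for 5 min, against the nominal 5%.
- If it is higher by b, power for a true 15 min effect = Φ((15 − b)/5.96 − 1.645). This gives 70% for b = 2 min and 51% for b = 5 min, against 81% with no shift.

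**6. If only some participants are affected.** The average shift shrinks in proportion. A 5 min shift in half of the participants averages 2.5 min (type I error 11.0%). In a quarter it averages 1.25 min (7.6%).

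The standard error takes the plan's SD as given. A larger SD would make the same shift matter less for type I error.

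**The case against.** Several points on the other side have force.

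- **The contrast.** The sub-study analysis text also speaks of planned contrasts between conditions at each time point. Read literally, a contrast of post-treatment values would not subtract the baseline. However, the same text compares from pre-treatment, and the power section defines each comparison as an interaction, so change is the likelier reading. Any part of the shift that persists to the later time point cancels.
- **The instrument.** A reader might infer that this week is the baseline for both primary outcomes. The documents do not establish that. They name no instrument for self-reported sleep quality, and Aim 2 needs a mid-treatment value when no diary is kept. The log does record sleep quality, so the diary may supply it. Actigraphic duration, which certainly uses this week, is probably the less suggestible of the two.
- **The wording.** Section D6s, under the diary heading, calls this week the pre-treatment assessment period, the term that section D6l lists as required. With the synopsis and Table 1, that supports a baseline-first reading. The stated Version 13 intention weighs against it, so the passages conflict and need reconciling.
- **Disappointment with the control.** Section D6n says consent presents education as one of three treatments and that past participants found it credible. This makes a large shift less likely but does not rule one out.
- **Cost of a gate.** Making an optional sub-study week a condition of randomisation could slow the main trial. The sub-study reports 27% attrition and expects 10% of actigraphs not to be returned. This objection stands, and the fix avoids such a gate.

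**Conclusion.** The timing gap is in the current text and appears deliberate. A sleep baseline recorded after randomisation, and probably after the participant knows the arm, is permitted, while other current passages imply the opposite order. Such a baseline can bias the Aim 1 change contrast for actigraphic sleep duration and, where the diary supplies it, for self-reported sleep quality.

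A reader might infer that the sleep results are biased, or that sub-study participants have been told their arm before the baseline. The documents support neither. They do not state how many baselines followed notice, what the letter discloses, or whether sleep shifts in response. The figures of about 7-21% type I error and about 51% power rest on an assumed average shift of up to 5 minutes (one third of the 15-minute target effect), on the plan's own SD, and on the shift having gone by follow-up. They show sensitivity and are not estimates.

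The point concerns the sub-study only. The main trial's initial pain-call week is on the list required before randomisation. The change is worth making because it is cheap and reaches a primary sub-study contrast.

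**What to change.** 1. Reconcile the Précis, the sleep sub-study design table and section D6s with the D1 synopses and Table 1, so that the sleep week ends before the participant is notified of assignment. Run it alongside the pain-call week where possible. Otherwise hold the assignment letter and the class appointment entry until it ends. Do not make it a condition of main-trial randomisation.
2. Record the date of notice against the dates of each sleep week and any repeat.
3. Pre-specify a sensitivity analysis of the Aim 1 contrasts restricted to participants with a pre-notice baseline week, using the earlier week where a repeat followed notice. Whether such a week exists is settled before the participant knows the arm, so the restriction should not itself unbalance the arms. This step remains useful if collection has already finished, provided the dates can be recovered.

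The cost is a delay of some days in sending the letter to some sub-study participants, one extra date field, and a smaller sample in the sensitivity analysis. For participants whose repeat followed notice, that analysis also gives up the plan's four-week limit on the age of the baseline. The sample size is unchanged at 39 per arm.
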